4.2 SCIENTIFIC RATIONALE FOR STUDY DESIGN

As part of the platform design, all participants will be screened for sleep-related breathing disorders (SRBD), including OSA, central sleep apnea (CSA), Cheyne-Stokes breathing, and sleep-related hypoxemia unexplained by OSA. These SRBDs are either exclusion criteria (CSA, Cheyne-Stokes breathing, unexplained hypoxemia) or, for OSA, a significant co-morbidity that must be assessed and managed before assessing eligibility for a specific sleep phenotype arm.³⁴ OSA, the most common SRBD, occurs in 9% to 38% of adults and leads to nightly, recurring acute hypoxemic episodes that can trigger a cascade of pathophysiological responses, including inflammation, autonomic and endothelial dysfunction, and oxidative stress. This cascade of responses can promote adverse physiology and symptom clusters relevant to PASC, including cardiometabolic disease, excessive daytime sleepiness, neurocognitive impairment (including "brain fog" as reported by patients with sleep apnea), and possibly lung injury.^{15,16,35,36} Although data are scant on OSA in PASC, among patients with acute SARS-CoV-2 infection, OSA is associated with an approximately 50% increased mortality rate in analyses adjusted for demographic factors; notably, no evident increased risk was observed in patients with treated OSA.³⁴ Importantly, and relevant to this clinical trial, untreated severe sleep apnea can negatively impact the efficacy of treatments for all other sleep disorders. In using wake-promoting medications, it is important to exclude untreated OSA or only use these medications in patients with hypersomnia who do not tolerate or fail primary treatment of OSA. Therefore, to test interventions targeting PASC-emergent sleep disturbances like insomnia and hypersomnia, it is important to screen for and exclude individuals with moderate or severe, untreated OSA and other severe SRBDs.

Each appendix will detail a different study intervention and design that targets the complex symptoms of PASC-emergent sleep disturbance. Study interventions may include pharmaceutical agents, hormones, behavioral interventions, light therapy, or non-traditional interventions. Additional study interventions may be added as new agents/interventions are proposed to address sleep disturbance issues in PASC.

4.3 JUSTIFICATION FOR DOSE

The dose and duration of the study intervention will be based on the specific intervention. Refer to the appendices for details.

4.4 END OF STUDY DEFINITION

The end of study will occur when all participants have completed the End of Study visit which is to be scheduled approximately 30 days after the participant has completed the study intervention period.

5 STUDY POPULATION

The following inclusion and exclusion criteria are the basic criteria for the platform protocol. Some appendices may have variations or criteria specific to their intervention. See appendices.

5.1 INCLUSION CRITERIA

In order to be eligible to participate in this study, an individual must meet all of the following criteria:

- 1. ≥18 years of age at the time of enrollment
- 2. Previous suspected, probable, or confirmed SARS-CoV-2 infection, as defined by the Pan American Health Organization:³⁷

Suspected* case of SARS-CoV-2 infection - Three options, A through C:

- A. Met the clinical OR epidemiological criteria:
 - a. Clinical criteria: Acute onset of fever AND cough (influenza-like illness) OR Acute onset of ANY THREE OR MORE of the following signs or symptoms: fever, cough, general, weakness/fatigue, headache, myalgia, sore throat, coryza, dyspnea, nausea, diarrhea, anorexia;
 - b. Epidemiological criteria: Contact of a probable or confirmed case or linked to a COVID-19 cluster; or
- B. Presented with acute respiratory infection with a history of fever or measured fever of ≥38 °C (100.4 °F) and cough, with onset within the last 10 days, and required hospitalization; or
- *C.* Presented with no clinical signs or symptoms, NOR meeting epidemiologic criteria with a positive professional use or self-test SARS-CoV-2 Antigen-Rapid Diagnostic Test.

Probable* case of SARS-CoV-2 infection, defined as having met the clinical criteria above AND was a contact of a probable or confirmed case or is linked to a COVID-19 cluster; or Confirmed case of SARS-CoV-2 infection - Two options, A through B:

- A. Presented with a positive nucleic acid amplification test, regardless of clinical criteria OR epidemiological criteria; or
- B. Met clinical criteria AND/OR epidemiological criteria (See suspected case A), with a positive professional use or self-test SARS-CoV-2 Antigen-Rapid Diagnostic Test.

* Suspected and probable cases will only be allowed if they occurred before May 1, 2021, and will be limited to 10% of the study population. Otherwise, confirmed cases are required.

- 3. New/worse sleep problems following a SARS-CoV-2 infection that have persisted for at least 12 weeks³⁸ and are still present at the time of consent
- 4. PROMIS 8a SRI or 8b SD T score ≥60
 - A. If the PROMIS 8a SRI is ≥60, participants must also self-report symptoms of trouble staying awake, feeling too sleepy, or falling asleep unintentionally during the day over the preceding 12 weeks, and these symptoms either started after a SARS-CoV-2 infection, or if they preceded a SARS-CoV-2 infection, must have mostly worsened since the infection. These PRO outcomes and patient responses suggest a hypersomnia phenotype.
 - B. If the PROMIS 8b SD is ≥60, participants must also self-report symptoms of trouble falling asleep, staying asleep, or frequently waking from sleep over the preceding 12 weeks, and these symptoms either started after a SARS-CoV-2 infection, or if they preceded a SARS-CoV-2 infection, must have mostly worsened since the infection.

These PRO outcomes and patient responses suggest an insomnia or circadian rhythm disorder phenotype.

- 5. Willing and able to provide informed consent, complete the surveys and clinical assessments, and return for all of the necessary follow-up visits
- 6. Adequate method of birth control for participants of child-bearing potential

5.2 EXCLUSION CRITERIA

An individual who meets any of the following criteria will be excluded from participation in this study (though participants may be re-screened at the site investigator's discretion):

- 1. Known active acute SARS-CoV-2 infection ≤4 weeks from consent
- 2. Known pregnancy, breastfeeding, or contemplating pregnancy during the study period
- 3. Untreated SRBDs
 - a) OSA (apnea hypopnea index/respiratory event index ≥15)
 - b) CSA (central apnea index \geq 10)
 - c) Cheyne-Stokes breathing >10 minutes)
 - d) percentage estimated sleep time at an oxyhemoglobin saturation <88% (T88) >10% unexplained by an elevated apnea hypopnea index
- 4. Current night or rotating shift work
- 5. Known history of narcolepsy prior to SARS-CoV-2 infection
- 6. Any non-marijuana illicit drug use within 30 days of informed consent
- 7. Known history of severe mental disorder, such as psychotic disorders and bipolar disorder
- 8. Current or recent use (within the last 14 days) of study intervention or similar intervention to treat the underlying condition, unless a washout period is permitted per appendix*
- Known allergy/sensitivity or any hypersensitivity to components of the study intervention or control*
- 10. Known contraindication(s) to study intervention including prohibited concomitant medications and without the ability to safely hold prohibited concomitant medications (see appendices)*
- 11. Currently receiving/using intervention from another clinical trial that could impact or mask treatment effect
- 12. Any condition that would make the participant, in the opinion of the site investigator, unsuitable for the study

* An exclusion from the platform protocol if only one study intervention appendix is open at the time of enrollment. If multiple study intervention appendices are open, a participant may be excluded from any study intervention appendix based on contraindications listed in the study intervention appendix, current use of study intervention, or known allergy/sensitivity/hypersensitivity yet remain eligible for the remaining study intervention appendices.

5.3 LIFESTYLE CONSIDERATIONS

Participants capable of becoming pregnant must agree to use an effective method of contraception during study intervention administration and for at least 7 days after the final administration of the study intervention. Effective methods include any of the following: abstinence, partner vasectomy, bilateral tubal ligation, intrauterine device, progestin implants, oral contraceptive pills, or barrier (condom, diaphragm, cervical cap) plus spermicide.

5.4 SCREEN FAILURES

Screen failures are defined as participants who consent to participate in the platform protocol but are not subsequently randomly assigned to an appendix study intervention. A minimal set of screen failure information is required to ensure transparent reporting of screen failure participants, to meet the Consolidated Standards of Reporting Trials (CONSORT) publishing requirements, and to respond to queries from regulatory authorities. Minimal information includes demography, screen failure details, and eligibility criteria. Individuals who screen fail may be referred to other RECOVER protocols.

5.5 STUDY DEFINITION OF ENROLLMENT

For this study, enrollment is defined as signing the platform and appendix consents and completing randomization.

5.6 STRATEGIES FOR RECRUITMENT AND RETENTION

The RECOVER Clinical Trial Data Coordinating Center (CT-DCC) will use an integrated strategy of coordinating with community organizations, the public, and clinical trial sites to identify and retain study participants. To ensure a diverse population is enrolled, strategies from prior successful initiatives will be refined and utilized. The study team will develop a comprehensive communication strategy involving print and social media, as well as leveraging existing organizational structures where possible, to educate the public on concerns about PASC and opportunities for clinical trial participation. Interested members of the public will be provided with information to contact a local site for potential participation.

Participants can be recruited and identified through outreach by participating sites. Site investigators, or their designee, may contact eligible participants to introduce the study and discuss study participation.

Participants may be recruited from other ongoing trials (eg, COVID-19 trials) if they opted-in to be contacted about future research opportunities. Co-enrollment in other trials must be approved by RECOVER-SLEEP leadership.

Finally, to support participant referral to actively enrolling trials, a series of invitation algorithms based on appendix-specific inclusion/exclusion criteria and participant-entered data may be used. Automatic invitations will be generated for participants who appear eligible based on trial interest, demographics, and medical history. Once participants accept the invitation and adequate consent is obtained, their information will be shared with the applicable study team.

Patient advocates who represent a diverse PASC community will be engaged in the study at every step. Patient advocates will serve as consultants to inform recruitment and retention strategies.

During the active study, study sites will maintain close connections with study participants.

6 STUDY INTERVENTION

6.1 STUDY INTERVENTION(S) ADMINISTRATION

6.1.1 STUDY INTERVENTION DESCRIPTION

See appendices.

6.1.2 DOSING AND ADMINISTRATION

See appendices.

6.2 PREPARATION/HANDLING/STORAGE/ACCOUNTABILITY

6.2.1 ACQUISITION AND ACCOUNTABILITY

The use of study intervention will be tracked by the sites. The sites will call participants at least once during the intervention period to monitor compliance with study intervention administration.

For appendices with a study drug, receipt and use will be handled, tracked by the sites, and stored in a safe and secure location to which only the site investigator and designated personnel have access. Participants will also be asked to bring any unused study drug with them to the End of Intervention Clinic Visit, as applicable.

For appendices with a study device, receipt and use will be accounted for by the sites. Additionally, some devices may have accountability measures built in.

See appendices for further details.

6.2.2 FORMULATION, APPEARANCE, PACKAGING, AND LABELING

See appendices.

6.2.3 PRODUCT STORAGE AND STABILITY

See appendices.

6.2.4 PREPARATION

See appendices.

6.2.5 DESTRUCTION

Used and unused study drug can be destroyed at the site according to accepted pharmacy practice and both local and national guidelines, using the site's destruction procedure. A copy of the drug destruction procedure should be maintained in the pharmacy section of the regulatory binder.

6.3 MEASURES TO MINIMIZE BIAS: RANDOMIZATION AND BLINDING

This platform protocol is designed to allocate participants into an intervention appendix based on their symptoms of sleep disturbance (see Figure 3). Within the appendix, participants will be randomly assigned based on the appendix study design. Site investigators and personnel will be informed as to which study intervention appendix participants are assigned, but they will be blinded to whether participants are receiving the active study intervention or control, when possible. Similarly, participants will be blinded to active intervention or control, when possible. Randomization will be stratified by the study site; other stratification factors may be considered per appendix.

6.3.1 UNBLINDING

As applicable per appendix, the participant, treating clinicians, and study personnel will remain blinded to study intervention versus control assignment until after the database is locked and blinded analysis is completed. Only the biostatistical team who is preparing closed-session reports will be unblinded. Unblinding will occur only if required for participant safety or treatment, at the request of the treating clinician. Refer to the Manual of Procedures (MOP) for further details.

6.4 STUDY INTERVENTION ADHERENCE

Participants will be notified of the importance of completing the full course of intervention.

6.5 CONCOMITANT THERAPY

Concomitant therapies to be reported in the Case Report Form (CRF) are relevant concomitant prescription medications, over-the-counter medications, and supplements taken by the participant within 14 days of the time point of interest. Note the following:

- Prescription medication is defined as a medication that can be prescribed only by a properly authorized/licensed clinician.
- Baseline concomitant medications will include all concomitant therapies taken by the participant within 14 days of informed consent.

7 PARTICIPANT DISCONTINUATION/WITHDRAWAL

7.1 PARTICIPANT DISCONTINUATION FROM STUDY INTERVENTION

Discontinuation from study intervention does not mean discontinuation from the entire study; thus, the remaining study procedures should be completed as scheduled by the study protocol. Participants will be asked to complete Early Termination Clinic Visit (Section 8.6). If a clinically significant finding is identified (such as changes from baseline) after enrollment, the site investigator or qualified designee will determine if any change in participant management is needed.

Site investigators may discontinue a participant from the study intervention at their discretion for any reason including, but not limited to, one of the following:

- Significant study intervention non-compliance
- Occurrence of any clinical adverse event (AE), laboratory abnormality, or other medical condition or situation such that continued participation in the study or study intervention would not be in the best interest of the participant

The reason for participant discontinuation from the study intervention will be recorded on the CRF. Participants who are discontinued from the study intervention, but who are not withdrawn from the study, will continue to be followed through all study procedures.

7.2 PARTICIPANT WITHDRAWAL FROM THE STUDY

Participants are free to withdraw from study participation at any time upon request. The study team will attempt to determine a reason for withdrawal; however, participants are not obliged to provide a reason. If obtained, the reason for withdrawal will be recorded on the CRF. No further study procedures will be performed and no further data will be collected from participants following study withdrawal. All data collected until the time of withdrawal will be maintained in the study database and used as participants' data are evaluable for analysis.

7.3 LOST TO FOLLOW-UP

Participants will be deemed lost to follow-up if they fail to return for any scheduled visit *and* cannot be contacted after multiple attempts and methods by the study site staff and/or a central search company.

The following actions must be taken if a participant fails to return to the clinic for a required study visit:

• The site will attempt to contact the participant and reschedule the missed visit, counsel the participant on the importance of maintaining the assigned visit schedule, and ascertain if the participant wishes to and/or should continue in the study.

- Before a participant is deemed lost to follow-up, the site investigator or designee will make every effort to regain contact with the participant or next of kin via telephone calls and, if necessary, a certified letter to the participant's last known mailing address or local equivalent. These contact attempts should be documented in the participant's medical record or study file.
- Should the participant continue to be unreachable, after exhausting all methods, he or she will be considered to have withdrawn from the study with a primary reason of lost to follow-up.

7.4 STUDY HALTING RULES

See appendices.

8 STUDY ASSESSMENTS AND PROCEDURES

8.1 SCHEDULE OF PROCEDURES

See the appendices.

8.2 PRE-RANDOMIZATION VISITS (WK -6 TO -1)

8.2.1 PRE-SCREENING

Interested patients who call a study site may be asked a series of questions to help determine if the study is a good fit for them and to reduce unnecessary physical and temporal effort and burden coinciding with a study visit. Patients who appear eligible may be scheduled for the Screening visit. Patients who are not eligible may be referred to another RECOVER study or re-screened based on the site investigator's discretion.

8.2.2 SCREENING

Information about the study will be presented to potential participants and questions will be asked to determine potential eligibility. *Study-specific screening procedures will begin only after informed consent for the platform protocol is obtained*. Informed consent may be obtained via paper or online forms.

The PROMIS 8a SRI and 8b SD will be the first procedure completed after obtaining consent. The PROMIS 8a SRI and 8b SD may be administered over the phone, by mail, in-person, or electronically. Both the 8a SRI and 8b SD will be administered, but which one serves the primary endpoint is defined in each appendix. Moreover, both will be completed as the first study procedure so that participants who score below 60 on both the 8a SRI and 8b SD (screen failure) will not be required to complete the remaining screening procedures. Conversely, participants who score 60 or greater on either the 8a SRI or 8b SD (eligible) will complete the Sleep-screening questions, which are several self-reported sleep-symptom questions. Based on their answers, they will screen fail or proceed to a sleep apnea history examination and the other screening procedures, which include the following:

- Demographics
- Concomitant medications, review of the previous 14 days
- Medical history, including SARS-CoV-2 infection history and PASC symptoms and duration

- Pregnancy test, urine or serum, for individuals of childbearing potential
- Nasal swab for SARS-CoV-2, using rapid antigen test or PCR test
- Screening blood labs, dependent on PROMIS 8a SRI and 8b SD scores

Screening procedures may be performed over 1 or 2 calendar days. Baseline assessments, specimen collection, and the initial study intervention administration can occur on the same calendar day. For some participants, SRBD¹ screening will reveal the need for further testing and treatment. This process (including HSAT device delivery, data collection, device return, data analysis, and treatment) may take 6 weeks or more.

All participants will undergo SRBD screening.

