8.3 BASELINE (DAY 0)

Baseline assessments may occur on the same day as Screening, depending on each patient's time availability and tolerance. If not on the same day, Baseline assessments may be divided into home and in-person assessments in order to reduce in-person burden time. For example, the PROMIS 8a SRI and 8b SD, secondary outcome measures, and exploratory PROs could be administered at home before the in-person visit, which would be used for completing the remaining assessments and procedures. Regardless of their order or location, the following assessments and procedures comprise the Baseline visit:

- Concomitant medications, collected for medications taken in the past 14 days, and alternative therapies
 - Only if the Screening review occurred more than 14 days prior
- Pregnancy test, urine or serum, for individuals of childbearing potential
 - o Only if the Screening test occurred more than 3 days prior
- Nasal swab, for SARS-CoV-2 using rapid antigentest or PCR test
 - Only if the Screening test occurred more than 3 days prior
- PROMIS 8a SRI and 8b SD
 - o Only if the Screening test occurred more than 7 days prior

- o If multiple assessments are performed, the most recent score is used for inclusion.
- Height and weight
 - Height may be obtained by self-report for participants who are unable to stand or by medical record.
 - Weight must be obtained from a scale.
- Sleep Phenotype questionnaire
- PROMIS 10a Fatigue
- Neurocognitive Battery
- ECog2
- PASC Symptom Questionnaire
- Insomnia Severity Index (ISI)
- Orthostatic Hypotension Questionnaire (OHQ)
- Modified DePaul Symptom Questionnaire-Post-Exertional Malaise (DSQ-PEM)
- Patient Global Impression of Severity (PGIS)
- SASS-Y, only for the Complex PASC-Related Sleep Disturbance appendix
- Sleep diary, distributed for participants to complete during pre-intervention
- Activity tracker, distributed for participants to wear during pre-intervention
- Blood collection, for clinical labs; timing and type may differ for each appendix
- Biorepository, for blood and stool; see Section 8.9
- Safety assessment, including serious adverse events (SAEs) and suspected unexpected serious adverse reactions (SUSARs)

See each appendix for additional procedures. Refer to the MOP for details of these procedures.

After completing Baseline assessments, participants will be randomized to an intervention group within their assigned appendix, which is based on their sleep phenotype.

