8.4 PRE-INTERVENTION AND INTERVENTION

8.4.1 PRE-INTERVENTION

Participants will complete the sleep diary and wear the activity tracker for 7 days. The activity tracker should be worn at all times during the 7 days except when charging. Other activities may occur according to each appendix.

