11.1.9 PROTOCOL DEVIATIONS

A protocol deviation is defined as non-compliance with the clinical study protocol or GCP requirements. The non-compliance may be on the part of the participant, site investigator, or site staff.

A major protocol deviation is a significant divergence from the protocol that may have a significant effect on the participant's safety, rights, or welfare and/or on the integrity of the study data. Major protocol deviations must be sent to the study IRB and local IRB per their guidelines, recorded in source documents, and reported to the coordinating center. All protocol deviations will be documented. Major protocol deviations will be tracked. For this study, any missed or delayed survey completion will not be considered a major protocol deviation, unless it is a study procedure required for the primary endpoint.

Failing to wear the activity tracker during the entire intervention is not a deviation; only the 7 days at the beginning and end of the intervention are required.

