Light-dark patterns are the major synchronizers of circadian rhythms to the local light-dark cycle, which influence sleep timing and quality. Insufficient exposure to morning light or exposure to high light levels in the evening or night can lead to circadian disruption, resulting in sleep-wake irregularity, poor sleep quality, poor cognitive performance, higher depressive symptoms, higher stress, and increased fatigue. Light in the built environment, especially at home, can be too low to entrain the circadian system during the day. Lack of entrainment or circadian misalignment may reduce the strength of circadian rhythms, and can also negatively impact immune function and inflammation. Melatonin is a hormone produced during darkness at night. It prompts appropriate nighttime behaviors and physiological functions including, in humans, sleep. Circadian misalignment may dysregulate melatonin production at night. Poor sleep and other symptoms may be improved by optimizing the alignment of a participant's circadian rhythms strengthening and alignment can be accomplished with the administration of appropriately-timed light in the morning and oral melatonin 2 hours before the scheduled bedtime.

1) The RESET-PASC educational component will be delivered by video (and/or paper brochures) and electronic reminders and will include content on optimal sleep habits, the role and use of melatonin and light for sleep, and recommendations on bedtimes (based on information on the sleep diary and the Split Week Sleep Assessment of Sleep (SASS-Y)).

Sleep onset variability, assessed from an activity tracker used for 7 days at Baseline and EOI, is an endpoint for only this appendix. Night to night sleep onset variability is an objective measurement that, when combined with the subjective PROMIS 8b SD, will help characterize the intervention's effect on CPSD. Further, sleep onset variability is a clinically interpretable and meaningful measure as it correlates strongly with overall sleep-wake variability (eg, sleep midpoint variability).

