14.4.2 LIGHT DELIVERY METHOD

The modified table/floor lamp will deliver polychromatic white light from up to 12-16 inches from the open eye for at least 1 hour in the morning (within 2 hours of waking, but no later than noon). The table/floor lamp is a controlled plug-in fixture that will be placed on a timer. The timer will be set to turn the light table on at desired wake times and turn it off 4 hours before desired bedtimes.

Participants will also wear a light sensor (Blue Iris Labs Mobile Sensor) to measure existing surrounding lighting during the intervention. The Blue Iris is a personal light meter calibrated to measure circadianeffective light. It can store 60 days of light measurements at 1-min intervals. It will characterize the light exposure of each participant. This light sensor will help verify compliance with the light exposure protocol. Importantly, the Blue Iris is noninvasive, not a medical device, and produces no harmful emissions. Similar to wearing a badge, participants will be asked to wear the device for the duration of the study, but at a minimum for 7 days after TL installation and 7 days before EOI. If they choose not to wear the Blue Iris device for the duration of the study, they will be asked to keep a daily log with the start and end times they were exposed to the intervention.

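### Appendix B's sleep onset variability baseline is recorded after randomization, and the protocol contradicts itself on whether that week is free of treatment

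*Protocol*

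**What the plan says.** **Order of events.** On Day 0 the tracker is only handed out (Section 8.3: "Activity tracker, distributed for participants to wear during pre-intervention"). Then "After completing Baseline assessments, participants will be randomized to an intervention group within their assigned appendix". Pre-intervention activities start within 48 hours, and in that period "Participants will complete the sleep diary and wear the activity tracker for 7 days" (Section 8.4.1). Table 3 agrees: randomization on Day 0, tracker worn in Wk 1. Section 14.1 makes this week the endpoint's baseline: "Sleep onset variability, assessed from an activity tracker used for 7 days at Baseline and EOI, is an endpoint for only this appendix".

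**Text that presents Wk 1 as untreated.** Sections 8.4.1 and 8.4.2 separate pre-intervention from intervention. Section 8.8.2.7 has the tracker worn for 7 days before the intervention. Table 3 marks use of capsules and light only from Wk 2. Sections 14.4.3 and 14.5.4 give 8 weeks of light and of melatonin, which fits Wk 2 to 9.

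**Text that permits exposure in Wk 1.**
- Section 8.2.2: "Baseline assessments, specimen collection, and the initial study intervention administration can occur on the same calendar day".
- Section 11.1.9, on tracker wear: "only the 7 days at the beginning and end of the intervention are required".
- Section 14.1 gives a 9-week intervention, and Table 3 ends at Wk 9, so Wk 1 is counted.
- Table 3 distributes lamp and capsules on Day 0 and installs the lamp in Wk 1. The light sensor is also worn in Wk 1, and Section 14.4.2 requires it "at a minimum for 7 days after TL installation and 7 days before EOI".

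**Analysis.** Section 10.4.2 plans ANCOVA on change with the baseline as covariate, and a similar approach for sleep onset variability. Section 10.4.1 leaves out of the primary analysis anyone who lacks either measurement.

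**The concern.** A baseline used as a covariate should not carry any treatment effect. If some of the Wk 1 nights follow lamp use or a first capsule, part of the effect is already in the baseline, and adjustment removes a share of it from the estimate. No passage says that the installed lamp stays off, or that the dispensed capsules stay unused, until the tracker nights are complete. A site that follows Section 8.2.2 or 11.1.9 literally would record on-treatment nights as baseline, and no later analysis could recover untreated nights that were never recorded.

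A second consequence needs no overlap. Because the week falls after randomization, a participant without a valid Wk 1 tracker week is lost from the primary analysis of this endpoint after having been randomized.

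The tracker and diary secondary endpoints in both appendices use the same Wk 1 baseline (Tables 2 and 3).

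**Working it through.** **1. Inputs from the protocol.** Two-sided alpha .025 per primary endpoint, effect size .35 to .45 and N = 600 (Section 14.8.1; two-sidedness from Section 10.4.1). SD 15, difference 5, planning R² about 0 and 20% attrition (Section 13.7.1, whose assumptions Section 14.8.1 largely adopts). Evaluable: 600 × 0.80 = 480. Quantiles: 2.2414 for alpha .025 and 1.2816 for 90% power.

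**2. The plan's own figures.**
- PROMIS 8b SD: 4 × 15² × (2.2414 + 1.2816)² / 5² = 446.8 evaluable, and 446.8 / 0.80 = 558.5. The stated 560 reproduces.
- Sleep onset variability at effect size .35: 406 evaluable, or 508 with attrition. So 600 is above the minimum, and the statement of at least 90% power is true. With 480 evaluable, Phi(.35 × √480 / 2 − 2.2414) = 94.4%.

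**3. Attenuation.** Let the true effect at EOI be delta, and let a fraction f of it be present in the baseline week. With b the within-arm slope of EOI on baseline, the ANCOVA estimate is

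delta − b × (f × delta) = delta × (1 − b × f),

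and b is about rho when the two variances are similar. This holds whether the response is the EOI value or the change. A simulation with 1,000,000 records at delta = .35 gave .296 for rho .5, f .3 (formula .2975) and .276 for rho .7, f .3 (formula .2765). A change score not adjusted for its own baseline would give delta × (1 − f), but that is not the planned analysis.

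**4. Size.** Neither f nor rho is in the protocol; the values below are assumptions. Power uses 480 evaluable and effect size .35. *Planning variance* is Phi(d × √480 / 2 − 2.2414). *Variance credited* divides the first term by √(1 − rho²), because a correlation large enough to attenuate the effect also reduces the residual variance.

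| f | rho | Effect estimated | Power, planning variance | Power, variance credited |
|---|---|---|---|---|
| 0 | 0.3 / 0.5 / 0.7 | .3500 | 94.4% | 96.2% / 98.6% / 99.9% |
| 0.1 | 0.3 | .3395 | 93.0% | 95.1% |
| 0.1 | 0.5 | .3325 | 91.9% | 97.5% |
| 0.1 | 0.7 | .3255 | 90.7% | 99.7% |
| 0.3 | 0.3 | .3185 | 89.4% | 92.2% |
| 0.3 | 0.5 | .2975 | 84.6% | 93.6% |
| 0.3 | 0.7 | .2765 | 78.5% | 97.7% |
| 0.5 | 0.3 | .2975 | 84.6% | 88.0% |
| 0.5 | 0.5 | .2625 | 73.7% | 86.0% |
| 0.5 | 0.7 | .2275 | 59.9% | 89.4% |

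The estimate keeps 97% (1 − 0.3 × 0.1) to 65% (1 − 0.7 × 0.5) of the effect. Crediting the variance reduction restores much of the power but none of the estimate.

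**5. Counting the weeks.** Appendix A gives a 10-week intervention (Section 13.1), and Table 2 runs to Wk 11, so Wk 1 is outside it. Appendix B gives 9 weeks, and Table 3 runs to Wk 9, so Wk 1 is inside it, although light and melatonin each last 8 weeks. The two appendices treat the same pre-intervention week differently.

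**The case against.** The best reply is that the operative schedule intends Wk 1 to be untreated. Table 3 has a separate pre-intervention column, and its Wk 1 lamp entry is installation, not use. The lamp runs on a timer, and the footnote on timer set-up belongs to Wk 2-8, while the one on installation concerns the light sensor. Capsules are timed to a scheduled bedtime. Bedtime recommendations draw on the sleep diary, which is completed in Wk 1, and the prescription for light and capsule times follows central review of survey data (Sections 14.1, 14.5.4, 14.6). Section 8.2.2 is a permissive platform sentence, Section 11.1.9 is shorthand in a deviation rule, and Section 14.4.2 concerns the light sensor rather than the endpoint tracker. The table footnote leaves exact timing to the MOP, which is not at hand.

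Much of this stands, and it makes untreated nights the likelier intention. It does not settle the matter, because the permissive sentences remain in the protocol and nothing in it bars exposure before the nights are complete.

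Three stronger readings are tempting, and the protocol does not support them:
- *The endpoint is biased toward zero as a matter of course.* A post-randomization baseline recorded under blinding and before exposure does not bias the effect; with f = 0 the attenuation is nil.
- *RESET-PASC Session 1 on Day 0 contaminates the comparison.* All four groups receive it, so it does not by itself separate the arms.
- *Power falls to about 74% at rho = f = 0.5.* That uses rho to attenuate the effect while holding R² at 0. Treated consistently, the figure is 86%.

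On missing tracker weeks, loss before exposure under blinding has no stated reason to differ by arm, and Section 10.4.1 plans imputation as a sensitivity analysis. The loss of randomized participants remains, but the protocol gives no rate from which to size it.

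**Conclusion.** The point holds as a contradiction with a conditional consequence. It is certain that the tracker baseline of this primary endpoint follows randomization, and that the protocol both presents Wk 1 as untreated and permits exposure in it. Bias toward zero arises only if exposure occurs in that week and active light or melatonin already lowers variability there. Its size is then about rho × f of the effect: 3% to 35% over the assumed ranges, with the power figures shown in the working. Those ranges are assumptions; the upper end of f supposes that half of the final effect is present in the first nights. The removal of randomized participants without a valid Wk 1 week applies in any case.

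**What to change.** 1. Define the analysis baseline for tracker and diary endpoints, in both appendices, as nights before first exposure to lamp or to capsule or tablet.
2. Record the dates of lamp activation and of the first dose, so that overlap can be checked for each participant.
3. Reconcile Sections 8.2.2, 8.4.1, 8.8.2.7, 11.1.9, 14.1 (9 weeks), 14.4.2 and Table 3 so that the nights used as baseline cannot overlap exposure. Which start-of-intervention rule applies is for the sponsor to settle; the passages must give the same answer.

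The cost is wording in the protocol and MOP and two date fields.

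Optionally, collect the 7 nights before randomization, within the existing Wk -6 to -1 window, and require usable nights before a participant is randomized. That would also prevent the loss of randomized participants for want of a baseline. Its cost is that some trackers go to later screen failures, or that randomization moves by about a week.
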